4.5. Pharmacodynamic Analysis and Correlation Analysis

Analyses will be conducted using the TP and SEP (if different than TP), or subgroups of TP as applicable, and will include summary tables with descriptive statistics and figures (all values versus time on x-axis), and displaying the items below:

- PB VCN over time will be summarized per time point, and by-subject spaghetti plots presented. Bone marrow and lineage cells VCN will be included in a listing only, if available.
- By-subject over time summaries and spaghetti plots for Group C will also be presented for exploratory analyses:
 - %LVV+ colonies over time
 - % β^{A-T87Q} + RBCs over time
- The following exploratory correlation analyses plots, but may not be limited to, will be conducted in TP:
 - Weighted average DP %LVV+ Cells vs weighted average DP VCN (TP overall)
 - PB VCN at Month 6 vs weighted average DP VCN (TP Group C)
- Hemoglobin fractions (including HbA^{T87Q}, HbA, HbA₂, HbS and HbF, as relevant, calculated using ratio data from HPLC and total Hb) are summarized by time point. Additionally, each fraction over time will be presented in a by-subject spaghetti plots separately for all subjects in TP. The ratios and total Hb used to derive the fractions will also be included in a by-subject listing.
 - HbA^{T87Q} = β^{A-T87Q} -Globin to All β -Like-Globin-Chains/100×total Hb
 - HbA = β^A -Globin to All β -Like-Globin-Chains/100×total Hb
 - HbA₂ = δ -Globin to All β -Like-Globin-Chains/100×total Hb
 - HbS = β^S -Globin to All β -Like-Globin-Chains/100×total Hb
 - HbF = (γ G-Globin to All β -Like-Globin-Chains + γ A-Globin to All β -Like-Globin-Chains)/100×total Hb
 - Ratio of α -globin to total of all β -like globins if data available

4.6. Safety Analysis

The safety analyses identified below will be performed on subjects in all 3 Groups in the ITT population or TP, as appropriate. Supportive figures will be provided as needed.

Because the safety profile will be assessed for several different time intervals (see [Section 3.11](#)) there may be subjects in the ITT population who are not eligible for analyses during some of these intervals. For example, if a subject has conditioning-regimen related events and does not receive drug product, that subject would not be considered in the analyses of safety data post-drug product infusion (i.e., Day 1 through Month 24 Visit).

4.6.1. Adverse Events

AE collection windows for Groups A and B are different than those for Group C, and the details can be found in [Section 1.2.1](#). All AEs will be coded via MedDRA coding system (version 23.0 or higher) and displayed in tables and listings using SOC and PT. The safety analyses will include evaluation of all AEs and of treatment-emergent AEs. The terminology "treatment-emergent" is reserved for events that occur during or after drug product infusion.

Summaries of AEs related to drug product will be based on the investigator's assessment; an assessment of 'Possibly Related', 'Related' or missing (if AE occurred after drug product

infusion) will be considered related to drug product. AEs will be summarized by the time intervals mentioned in [Section 3.11](#). For treatment-emergent AEs, only the following time intervals will be presented: "D1 to <NE" which is from drug product infusion to the latest date prior to initiation of neutrophil engraftment, "NE to M24", and "D1 to M24". The number of subjects "at risk" in each time interval will also be provided in summary tables. Subjects who are lost to follow-up, withdrew from the study, or died prior to the beginning of the time interval will be excluded from the number "at risk" in the time interval.

Summary information (the number and percentage of subjects by SOC and PT, separated by group and by time interval) will be tabulated for:

- All AEs
- Treatment-emergent AEs
- Serious AEs (SAEs)
- Treatment-emergent SAEs
- Grade 3 or higher AEs
- Grade 3 or higher treatment-emergent AEs
- Treatment-emergent AEs related to drug product
- Treatment-emergent SAEs related to drug product
- AEs attributed to SCD
- AEs attributed to SCD post Month 6
- SAEs attributed to SCD
- SAEs attributed to SCD post Month 6
- AEs attributed to cell procurement (bone marrow harvest ^[1] and mobilization/apheresis ^[1])
- Grade 3 or higher AEs onset within 7 days post plerixafor
- AEs attributed to conditioning ^[1]
- AEs attributed to study procedure ^[1]
- AEs from Informed Consent to Month 24 visit by selected subgroups (as specified in [Section 3.8](#) as appropriate), to be presented in two time intervals: "ICF to M24" and "D1 to M24".
- AEs by maximum severity (overall and by selected subgroups)
- Events of interest (search criteria in [Appendix 6.7](#))

^[1] Based on attribution on CRF for events as reported by investigators

A summary for all AEs will also be tabulated by PT, separated by group and time interval. The AEs will be presented according to descending frequency PT in overall group.

Listings will also be provided for all AEs, deaths, SAEs, AEs related to drug product, AEs leading to discontinuation, AEs attributed to study procedure, AEs attributed to BMH, AEs attributed to mobilization/apheresis, AE attributed to conditioning, and events of interest.

Events related to malignancy

The number and percentage of subjects with insertional oncogenesis (e.g., myelodysplasia, leukemia, lymphoma), in which LVV-insertion is demonstrated as likely to have contributed to the root cause of the malignancy will be summarized over time. Details will be presented in a by-subject listing. Malignancies will be reviewed via the bluebird bio safety governance process to determine the root cause and if any event meets the insertional oncogenesis endpoint.

Acute and/or chronic GVHD assessed by investigator

Number and percentage of subjects with acute and/or chronic GVHD assessed by investigator will be summarized. Details will be presented in a by-subject listing.

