6.2.30. Adverse Events

6.2.30.1. Assessments During Study

Monitoring of AEs will be conducted from the signing of informed consent. Adverse events, as defined in [Section 6.2.30.2](#) will be documented from the time informed consent is signed through the following time points for Groups A and B:

- \geq Grade 1 AEs: through 30 days after drug product infusion.
- \geq Grade 2 AEs: through 12 months after drug product infusion.
- All serious adverse events (SAEs), \geq Grade 3 AEs, and drug product-related AEs: through 24 months after drug product infusion.

For Group C, AEs for all subjects (excluding screen failures) will be recorded in the CRFs starting from the time informed consent is signed through the Month 24 Visit. All SAEs (including screen failures) will be reported from the signing of informed consent/assent on the SAE report form. Group C subjects enrolled under Version 7.0 of Protocol HGB-206 will have AEs retrospectively documented to be in accordance with Version 8.0 and Version 9.0 of Protocol HGB-206.

All AEs should be monitored until they are resolved or are clearly determined to be due to a subject's stable or chronic condition or inter-current illness(es). See also [Section 4.5](#) for AE monitoring of subjects who withdraw from the study.

For subjects who withdraw for reasons other than withdrawal of consent, any SAEs open at the time of discontinuation should be followed up until resolution or are determined to be a stable or chronic condition. If withdrawal is before drug product infusion, subjects should remain on study for at least 30 days after any invasive study procedure (e.g., mobilization, liver biopsy) before withdrawal and ongoing AEs should be monitored for the 30-day duration. In the rare case a subject undergoes myeloablation and receives back-up cells instead of bb1111, subject should remain on the study for at least 3 months post-myeloablation and AEs should be followed for the 3-month duration.

If withdrawal is after drug product infusion, subjects will be asked to complete the same assessments as specified in the SOE for Month 24 (Early Termination Visit assessments) and are expected to enroll in the long-term follow-up study.

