- Group C: Opened after (1) confirmation of the safety and tolerability of plerixafor mobilization in Group B2, and (2) regulatory authority approval of the drug product manufacturing process with plerixafor-mobilized hematopoietic stem cells (HSCs). In Group C, both drug product and back-up cells are derived from plerixafor mobilization and apheresis, and drug product is manufactured using Process 2a.

Monitoring of adverse events will be conducted from the signing of informed consent.

- For Groups A and B: adverse events will be documented from the time Informed Consent is signed through the following time points:
 - \geq Grade 1 AEs: through 30 days after drug product infusion.
 - \geq Grade 2 AEs: through 12 months after drug product infusion.
 - All serious adverse events (SAEs), \geq Grade 3 AEs, and drug product related AEs: through the end of study.
- For Group C: all AEs for all subjects (excluding screen failures) will be recorded in the Case Report Form (CRF) starting from the time Informed Consent is signed through the end of study. All SAEs (including screen failures) will be reported from the signing of Informed Consent/Assent through end of study on the SAE report form. Group C subjects enrolled under Version 7.0 or earlier of Protocol HGB-206 will have AEs retrospectively documented to be in accordance with Version 8.0 or higher of Protocol HGB-206.

For subjects in all 3 Groups who initiated any stem cell collection procedures (mobilization/apheresis or bone marrow harvest), all investigator vaso-occlusive events (VOEs) occurring on or after the signing of Informed Consent/Assent, regardless of the severity grade, will be documented from the time informed consent is signed through the last follow-up of the study. For subjects enrolled under Version 7.0 of Protocol HGB-206, the VOEs will be retrospectively documented to be in accordance with Version 8.0 or higher of Protocol HGB-206.

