3.5. Methods of Pooling Data

Data will be presented by group. Efficacy analyses will focus on Group C. However, an overall column will be included as appropriate.

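### In intervals running to Month 24, the overall adverse-event columns count Groups A and B as at risk for low-grade events those groups no longer recorded, so pooled low-grade frequencies are understated, by at most 20% in relative terms

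*SAP*

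**What the plan says.** **Collection.** Protocol 6.2.30.1 and SAP 1.2.1 give Groups A and B a tiered scheme. The lowest tier is "Grade 1 AEs: through 30 days after drug product infusion", the next is "Grade 2 AEs: through 12 months after drug product infusion". The top tier covers all serious events together with "Grade 3 AEs, and drug product-related AEs: through 24 months after drug product infusion" (Protocol); the SAP puts its end at study end instead. For Group C the Protocol records all adverse events "starting from the time informed consent is signed through the Month 24 Visit". Group C subjects enrolled under protocol Version 7.0 have events documented retrospectively to match later versions. No such step is stated for adverse events in Groups A and B.

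**Analysis.** SAP 4.6 places all three groups in the safety analysis. SAP 4.6.1 acknowledges the different windows ("AE collection windows for Groups A and B are different than those for Group C") and refers back to SAP 1.2.1, but gives no rule for handling them. The number at risk in an interval excludes only subjects lost to follow-up, withdrawn or dead before the interval begins. The intervals include NE to M24, D1 to M24 and ICF to M24.

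**Display.** The tables are split by group. SAP 3.5 adds: "However, an overall column will be included as appropriate". For the preferred-term table, SAP 4.6.1 states: "The AEs will be presented according to descending frequency PT in overall group".

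**The concern.** A percentage is interpretable only if everyone in its denominator could have been counted in its numerator. For part of each late interval, a Group A or B subject who has a first occurrence of a non-serious, unrelated, low-grade event is at risk on paper and invisible in the data. In a pooled column this pulls the frequency in one direction only, downward.

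The outputs exposed are the overall columns, in late intervals, of these tables:

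- all adverse events and treatment-emergent adverse events;
- events attributed to sickle cell disease, including the version restricted to after Month 6;
- events attributed to conditioning or to study procedures;
- the subgroup tables;
- the maximum-severity tables.

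The post-Month-6 table shows the effect most plainly. Between Month 6 and Month 24, Groups A and B can contribute no non-serious, unrelated Grade 1 event, and can contribute Grade 2 events for only 6 of the 18 months. In the maximum-severity tables, the pooled Grade 1-2 share is lowered by collection rather than by outcome.

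What is at stake is the description of the late low-grade burden, and the order in which terms are listed. No hypothesis test or success criterion is involved.

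**Working it through.** **No plan figure to reproduce.** Neither document states an adverse-event frequency, so the check is of the size of the dilution.

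**Inputs**

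- Infused subjects (SAP Table 1): Group A 7, Group B1 1, Group B2 1, Group C 36. Groups A and B: 7 + 1 + 1 = 9. Total: 9 + 36 = 45. Share: 9/45 = 20%.
- Planned size (Protocol 4.1): 9 in Groups A and B plus about 41 in Group C. Share: 9/50 = 18%.
- Length of D1 to M24: 731 days, the 24-month figure in SAP 4.4.3.3.
- Collection in Groups A and B for non-serious, unrelated events: 30 days (Grade 1) and 365 days (Grade 2).

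**Uncollected share of D1 to M24 in Groups A and B**

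- Grade 1: (731 - 30)/731 = 95.9%
- Grade 2: (731 - 365)/731 = 50.1%

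**Pooled frequency.** Let p be the true per-subject incidence over D1 to M24, taken as equal in all groups, and q the incidence that Groups A and B can record. Then:

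pooled = (36p + 9q)/45

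**Upper bound.** If the term arises only outside the Group A and B windows, q = 0 and pooled = 36p/45 = 0.80p. A true 50% becomes 40%. The relative understatement cannot exceed 20% (18% at the planned size).

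**Illustration under an assumed constant hazard.** q = 1 - (1 - p)^(t/731), with t = 30 for a Grade 1-only term and t = 365 for a Grade 2-only term. For p = 30%:

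- Grade 1-only: q = 1.5%; pooled = (36 × 0.30 + 9 × 0.015)/45 = 24.3%, which is 5.7 points low.
- Grade 2-only: q = 16.3%; pooled = (36 × 0.30 + 9 × 0.163)/45 = 27.3%, which is 2.7 points low.

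| True p | Grade 1-only, pooled | Relative | Grade 2-only, pooled | Relative |
|---|---|---|---|---|
| 10% | 8.1% | -19.1% | 9.0% | -9.8% |
| 20% | 16.2% | -19.1% | 18.1% | -9.5% |
| 30% | 24.3% | -19.0% | 27.3% | -9.1% |
| 50% | 40.6% | -18.9% | 45.9% | -8.3% |
| 80% | 65.3% | -18.4% | 75.0% | -6.2% |

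With 9 of 50, the ranges are 16.6-17.2% (Grade 1-only) and 5.6-8.8% (Grade 2-only).

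**Unaffected outputs.** Serious, Grade 3 or higher and drug-product-related events are collected to Month 24 in every group, so their pooled tables stand. Intervals ending by Day 30 stand. D1 to <NE is touched only if engraftment falls between Day 31 and Day 43.

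**The case against.** The case against has real force.

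- **The gap is narrow.** Drug-product-related Grade 1-2 events are collected late in all groups, so only non-serious, unrelated ones are missing.
- **D1 to M24 includes time when Groups A and B do record low-grade events.** The tables count subjects, so one early occurrence of a term counts that subject in full. The conditioning effects that Protocol 6.2.30.2 expects, such as mucositis, nausea and alopecia, would largely start while every group is still collecting.
- **By-group display is already planned**, and the Group C column is clean.
- **The overall column is discretionary** under SAP 3.5, and the window difference is disclosed at the head of SAP 4.6.1.
- **Other outputs help.** SAP 1.2.1 has vaso-occlusive events recorded in all groups regardless of severity, and SAP 4.6.3 shows laboratory shifts beyond Month 12.
- **No decision depends on these tables.**

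All of this limits the point, and none of it removes it. A correct Group C column does not correct the overall column beside it, and disclosure leaves the pooled number unchanged. SAP 3.5 does not say when an overall column is appropriate for adverse events, and the preferred-term table uses the overall group explicitly. The SAP has also applied the needed principle elsewhere: SAP 4.4.3.2 confines change in transfusions to Group C because the baseline was collected only there.

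**Conclusion.** The point holds as a minor, one-directional bias in descriptive tables. Followed as written, the plan understates pooled frequencies of low-grade, non-serious, unrelated events in the intervals to Month 24, and ranks preferred terms on those frequencies. The ceiling is 20% relative (18% at the planned size). Under a constant hazard, the figures are about 18-19% for Grade 1-only and 6-10% for Grade 2-only terms.

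These sizes assume equal true incidence across groups and use infused subjects, because the Group C intent-to-treat count is not given. Within a subgroup, the ceiling is the Group A and B share of that subgroup, which is also not given. Terms that mix grades, or that mostly start early, lose less.

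Four stronger readings are tempting and are not supported:

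- **That Groups A and B record no low-grade events late.** They record drug-product-related ones to Month 24.
- **That their low-grade events cannot enter the D1 to M24 numerator.** Those starting inside the collection windows do.
- **That 20% is the expected loss.** It is reached only for terms arising solely outside the windows.
- **That the most common terms will change order.** The sort key is affected, but without adverse-event frequencies no reordering can be shown.

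**What to change.** Amend SAP 4.6.1 for intervals extending past Day 30:

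1. Give an overall column only for event classes collected in all groups: serious, Grade 3 or higher, and drug-product-related events.
2. For all-grade tables, keep the by-group columns already planned and omit the overall column.
3. Order preferred terms by Group C frequency.
4. Footnote the Group A and B collection windows on every all-grade table. The Group A and B columns carry the same under-collection, so a comparison with Group C is affected too.

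With Group C as the reference for the affected rows, the understatement from this source is zero. The cost is SAP wording and table shells, with no new data. The price is that no pooled all-grade figure will exist for the late intervals.

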4.6.2. Engraftment

All analyses in this section will be based on the TP unless otherwise specified.

Neutrophil engraftment (NE)

- Incidence of successful NE: defined as having 3 consecutive ANC values that are $\geq 0.5 \times 10^9/L$ obtained on different days after the initial post-transplant nadir by Day 43, without receiving back-up cells at any time during the neutropenic phase.
- Time to NE: defined as relative days from drug product infusion date to the first day of the 3 consecutive ANC laboratory assessments that meet NE criteria. It will only be calculated among subjects who had successful NE.

The proportion of subjects who achieved NE will be provided. The Rel Day of NE will be descriptively summarized. A scatter plot with regression line will be provided for Time to NE (in Days) against total cell dose of CD34+cells to explore their correlation.

Platelet engraftment (PE)

- Incidence of successful PE: defined as having 3 consecutive platelet values that are $\geq 50 \times 10^9/L$ obtained on different days after the initial post-transplant nadir, without receiving any platelet transfusions for 7 days immediately preceding and during the evaluation period
- Time to PE: defined as relative days from drug product infusion date to the first day of the 3 consecutive platelet assessments that meet platelet engraftment criteria. It will only be calculated among subjects who had successful PE.

The proportion of subjects who achieved PE will be provided. The Rel Day of PE will be descriptively summarized. A scatter plot with regression line will be provided for Time to PE (in Days) against total cell dose of CD34+cells to explore their correlation.

Supplementary Analyses for Time to PE

The following Supplementary analyses will be conducted:

Analysis Population	Supplementary Analysis
TP or TPVOE	For subjects who took eltrombopag before achieving PE, the Time to PE will be extended to one day after the end day of eltrombopag administration.

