5.8.2. Concomitant Medications and Therapies

All concomitant medications and therapies (i.e., those that are taken by the subject after signing the informed consent form [ICF]) should be documented.

Instructions and/or restrictions regarding specific concomitant medications and therapies are listed below. Concomitant medications and therapies not explicitly listed below may be used at the discretion of the treating physician and as per local standard of care.

- Granulocyte colony stimulating factor (G-CSF): G-CSF should not be used prior to Day 43 without explicit approval from the bluebird bio Medical Monitor.
- Venous access: Subjects will have appropriate long-term central venous access placed, per institutional standard practice, prior to beginning the preparative regimen. For subjects planned to undergo apheresis, placement of central venous access prior

to the first dose of plerixafor is strongly advised. For access, a double lumen tunneled catheter is recommended.

- Hydroxyurea: Hydroxyurea must be discontinued at least 30 days prior to stem cell harvest. It may be restarted between completion of the stem cell harvest(s) and admission to the hospital for myeloablation but should be stopped again at least 2 days before initiating myeloablation. Following HSC transplant, HU is not permitted without prior discussion with and explicit approval of the Sponsor's Medical Monitor.
- Erythropoietin: Erythropoietin is excluded and must be discontinued 60 days prior to stem cell harvest, as it may prevent engraftment of the transduced cells. Following HSC transplant, erythropoietin is not permitted without prior discussion with and explicit approval of the Sponsor's Medical Monitor.
- L-glutamine, crizanlizumab, and voxelotor: Following HSC transplant, medications other than blood transfusions to treat sickle cell disease or anemia (e.g., HU, erythropoietin, L-glutamine, crizanlizumab, voxelotor) are not permitted without prior discussion with and explicit approval of the Sponsor's Medical Monitor.

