prior to and (if possible) within 48 hours of transfusion. Subjects are recommended to continue transfusions during the pancytopenia phase to maintain Hb \geq 8 g/dL. For subjects who were on a chronic transfusion regimen prior to study entry, once engrafted and discharged post-transplant, it is recommended that the frequency of routine pRBC transfusions be adjusted to maintain Hb \geq 8 g/dL. Simple transfusions are recommended during this phase of follow-up and the period between transfusions will gradually be increased while maintaining safe HbS levels. Continued transfusion needs $>$ 6 months post-treatment or any alternative plans should be discussed with the Medical Monitor. Following HSC transplant, medications other than blood transfusions to treat sickle cell disease or anemia (e.g., HU, erythropoietin, L-glutamine, crizanlizumab, voxelotor) are not permitted without prior discussion with and explicit approval of the Sponsor's Medical Monitor.

- Platelet transfusion parameters: during the hospitalization for transplantation, platelets should be transfused to maintain a platelet count of $>$ 50,000/ μ L until platelet engraftment. After hospital discharge, subjects should get platelet count monitored approximately weekly and at least 8 days after the most recent platelet transfusion until platelet engraftment. Platelet engraftment is defined as 3 consecutive platelet count laboratory values \geq $50 \times 10^9/L$ obtained on different days while no platelet transfusions administered for 7 days immediately preceding and during the evaluation period. The day of platelet engraftment is the first day of the 3 consecutive platelet measurements.
- Blood pressure in patients with SCD is often lower than "normal" for age. Subjects should be closely monitored and antihypertensive medications started at the earliest sign of hypertension to maintain blood pressure (both systolic and diastolic) within 20% of the baseline.
- Other concomitant therapies during conditioning may include hyperdiuresis, prophylactic or therapeutic administration of anti-emetics, and veno-occlusive disease prophylaxis, e.g., ursodeoxycholic acid.
- See also next [Section 5.8.3](#) for infection prophylaxis.

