4.6.2	Engraftment	Added a supplementary analysis for time to PE. This is to extend the time to PE for subjects who took eltrombopag before achieving PE to align with the label.
4.6.3	Laboratory Data	Added hematology RDW test. Added the analysis of cytopenia.
4.6.7	Persistent Oligoclonality and Integration Site Analysis (ISA)	Updated the algorithm used for ISA to align with Protocol Version 13.0.
6.1	Imputation Rules for Missing Data	Updated the imputation rule for AE end date by replacing data cut-off date with last follow-up date. Updated the imputation rule for missing adjudicated VOE end date.
6.2	Analysis Visit Windows	Added analysis visit window for RDW.
6.7	Search Strategy for Events of Interest	Added thromboembolic events

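### The supplementary eltrombopag rule dates platelet engraftment by the last dose, with no off-drug platelet count required and no off-drug incidence reported

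*SAP*

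**What the plan says.** Protocol 5.8.2 defines PE as three consecutive platelet counts of at least 50 × 10⁹/L, "obtained on different days while no platelet transfusions administered for 7 days immediately preceding and during the evaluation period", and dates it as follows: "The day of platelet engraftment is the first day of the 3 consecutive platelet measurements". SAP 4.6.2 uses the same count threshold, adds that the counts follow the post-transplant nadir, and keeps the transfusion condition: "without receiving any platelet transfusions for 7 days immediately preceding and during the evaluation period". Neither definition has a condition on eltrombopag, and the protocol text does not mention the drug.

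For time to PE, the SAP states: "It will only be calculated among subjects who had successful PE". The supplementary analysis, in the TP or TPVOE, then applies to a subset, "For subjects who took eltrombopag before achieving PE", and the instruction is that "the Time to PE will be extended to one day after the end day of eltrombopag administration". SAP 5.2 gives the reason: "This is to extend the time to PE for subjects who took eltrombopag before achieving PE to align with the label".

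**The concern.** Both documents discount transfusion-supported counts, so the PE date is meant to mark a level that the subject holds without transfusion. The supplementary analysis appears to extend that idea to eltrombopag, since it treats a PE date reached on the drug as too early. But it replaces that date with the day after the last dose and does not ask whether the counts on or after that day satisfy the definition.

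Whether and how fast the stem cells engraft is a listed safety endpoint (Protocol 2.2.3, SAP 1.2.6.6). The subjects affected are those who received platelet support before PE. For them, the analysis meant to give a more cautious picture may still report a date that is too early. It also never says how many of them showed PE without the drug.

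**Working it through.** The documents give no figure for engraftment to reproduce, so the check applies the rules as written to assumed platelet series. All counts below are assumptions (× 10⁹/L, no platelet transfusions).

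**Rules applied**
- Main PE: first day of three consecutive counts ≥ 50 (Protocol 5.8.2, SAP 4.6.2).
- Supplementary PE: last eltrombopag day + 1 (SAP 4.6.2).
- Comparator: the main rule applied only to counts after the last eltrombopag day.

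**Series**
- A: drug ends Day 60. Days 20, 27, 34: 18, 30, 42. Days 40, 47, 54: 55, 60, 63. Days 61, 68, 75, 82: 44, 35, 38, 47. Days 90, 97, 104: 56, 60, 66.
- A2: series A stopped at Day 82, with no recovery observed.
- B: drug ends Day 20. Days 10, 17, 24, 31: 12, 20, 31, 40. Days 38, 45, 52: 52, 58, 61.

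| Series | Main PE | Supplementary rule, literal | Off-drug counts |
|---|---|---|---|
| A | Day 40 | 60 + 1 = Day 61 | Day 90 |
| A2 | Day 40 | 60 + 1 = Day 61 | not met |
| B | Day 38 | 20 + 1 = Day 21 | Day 38 |

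**Reading the table**
- In A, the count on Day 61 is 44, so Day 61 cannot be the first of three qualifying counts. The supplementary date is 90 − 61 = 29 days before the off-drug date.
- In A2 the subject has a supplementary time of Day 61 although no off-drug count reaches 50. Incidence also counts the subject as a success, because that status comes from the main definition.
- In B the drug stopped before PE. Read literally, the rule gives a date 38 − 21 = 17 days before the main PE date.

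**Drug still ongoing.** SAP 4.6.2 has no rule. Table 11 sets a missing medication end date to data cut-off or end of study, but under a heading about supporting VOE analyses. If it did apply, PE would fall one day after that date.

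**Weight of one subject.** SAP 4.6.2 uses the TP. Table 1 of the SAP gives 7 + 1 + 1 + 36 = 45 infused, so one subject is 1/45 = 2.2 percentage points of incidence.

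**The case against.** Several points on the other side stand.

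- A reader might infer that the rule checks no platelet count at all. It does: time to PE exists only for subjects who already have three qualifying transfusion-free counts. What is missing is an off-drug check.
- A reader might also infer that this rule makes a subject count as engrafted. It does not. Status comes from the main definition, which has no eltrombopag condition; the supplementary rule changes time only.
- The word *extended*, repeated in SAP 5.2, argues against ever moving the date earlier. Series B is therefore a wording gap that one clause would close, not a likely intention.
- Poor late recovery is not hidden. SAP 4.6.3 plans a summary of Grade 3 or higher cytopenia, platelets included, on or after Day 60 and Day 100. It flags platelets at or below 75 × 10⁹/L as potentially clinically significant, and it tabulates shifts using the lowest value per period. The unadjusted time to PE is also still reported. None of these outputs, however, revises the PE date or status.
- It is tempting to ask for a matching neutrophil analysis for G-CSF. The documents do not support that: Protocol 5.8.2 says "G-CSF should not be used prior to Day 43 without explicit approval from the bluebird bio Medical Monitor", Day 43 is also the neutrophil engraftment deadline, and concomitant medications are already tabulated from infusion to neutrophil engraftment (SAP 3.11 and 4.2.4).
- Borrowing the 7-day transfusion interval as an eltrombopag washout has no basis in the documents.
- Off-drug dating will be coarse. Protocol 5.8.2 asks for roughly weekly counts after discharge only until PE. After that, the follow-up schedule has visits at Days 60, 90, 135, 180 and 270, which are 30 to 90 days apart.

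**Conclusion.** The point holds in a limited form. The supplementary date is not tied to any off-drug platelet count, and PE incidence is never re-derived off drug. A subject who met the criterion only on eltrombopag and then fell below 50 × 10⁹/L receives an engraftment date on which the definition is not met. Read literally, the rule could also place PE before the main date when the drug stopped earlier.

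The size cannot be stated in total, because the documents do not say how many subjects took eltrombopag or what happened to their counts. The 29-day gap rests on an assumed series with weekly counts. The 2.2 points per subject apply to an off-drug incidence that is not now planned, not to the incidence already defined; 1/36 = 2.8 points would apply only to a Group C column. The analysis is descriptive and tests no hypothesis, so this affects how the safety endpoint is read, not any success criterion.

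**What to change.** In SAP 4.6.2, keep the label-aligned line, stating that it never gives a date before the main PE date, and add a second supplementary line for subjects who took eltrombopag before PE:

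- Re-apply the full PE definition (three consecutive counts of at least 50 × 10⁹/L on different days, transfusion-free as already defined) using only counts taken after the last eltrombopag dose. If an analysis washout is wanted, the sponsor should pre-specify its length and the reason.
- Take the later of that date and the main PE date.
- Report subjects who never meet the criterion off drug, or are still on drug, as not having shown unassisted PE. This means not shown, which is not the same as failed.
- Give both incidence and time, and the number of eltrombopag users.
- Show, per subject, the interval from the last drug day to the first qualifying count.

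No G-CSF analysis is needed.

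The cost is SAP wording and programming on platelet and medication data already collected. The downside is coarser dates: with scheduled visits only, three consecutive counts starting at Day 90 run to Day 180, and a short fall between visits could be missed. Incidence and time may look somewhat less favourable, which is why the interval should be shown beside the date.
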